### **3.0 Introduction and background**

Thymic epithelial tumours (TETs or thymic malignancies) which comprise thymoma and thymic carcinoma, are rare cancers worldwide. The annual incidence is approximately 0.15/100.000 in the United States (1) and 0.32/100.000 in the Netherlands (2). According to the Swedish National Cancer Register 33 patients were diagnosed with either thymoma or thymic carcinoma in 2013 which is an approximative incidence of 0.33/100.000. TETs are heterogenous both morphologically as well as clinically. Thymomas may be associated with a spectrum of autoimmune conditions, whereas this is rare in thymic carcinomas. Thymic carcinomas are more prone to distant metastatic spread. In a Japanese retrospective analysis the survival rates differs between the groups with a median OS of patients with thymoma of 235 months compared with 32 months for those with thymic carcinomas (3) which is comparable with other reports. There is no official stage classification for thymic malignancies defined by the Union Internationale Contre le Cancer (UICC) and the American Joint Commission for Cancer (AJCC). ITMIG in collaboration with the International Association for the Study of Lung Cancer (IASLC) have published a proposal for a new staging system for the forthcoming edition of the TNM classification of Malignant Tumors (4-5). Until this system is

definitely defined ITMIG has proposed staging according to the Masaoka-Koga stage classification (6) which is generally spread and used worldwide.

Surgery remains the cornerstone in the management of TETs. Minimally invasive techniques including thoracoscopic and robotic surgery for early stage disease are gradually increasing. Chemotherapy, although often with a moderate response, has a role in downstaging as well as managing more advanced disease. There is also evolving data on targeted drugs. The role for radiotherapy is a matter of ongoing debate but the use of postoperative radiotherapy (PORT) after incomplete surgery and/or advanced stage (III/IV according to Masaoka) is more or less standard (7-9). There is considerably less evidence and weaker consensus for the efficacy of PORT of stage II patients (10) and the use of it varies worldwide. It could, however, be used in selected cases such as B3 and C patients in accordance with local routines.

Radiotherapy with photons for TET patients has been reported feasible and with acceptable toxicity. Treatment is generally given with IMRT-technique and doses in the literature varies between 45 and 60 Gy with 1.8 or 2 Gy/fraction.

Many of the thymoma patients will become long time survivors and thus may suffer from late toxicities such as radiation induced lung disease (RILD) (11) or radiation induced heart disease (RIHD) (12-13). For many years RIHD has been of major concern when irradiating patients with left-sided breast cancer and Hodgkin's disease. It is considered a late side effect which may become manifest 5-10 years after completion of radiotherapy, although earlier onset may occur. It includes a wide range of symptoms such as pericarditis, myocardial infarction, valvular heart disease and coronary heart disease (14-15). Lately this has become a greater concern when treating thoracic malignancies such as lung and esophageal cancer (16). Depending on the good prognosis, there is a strong rationale as to try to limit the cardiac dose to the thymoma patients. Comparing treatment plans for protons vs photons has shown that it is possible to reduce the cardiac dose with protons (personal communication [name] & [name]).

How to detect and follow-up on RIHD is an ongoing subject for discussion. Different imaging techniques have been suggested (17-18) and there is also some data on biomarkers predicting cardiac toxicity after chemotherapy and radiation therapy (19). There is, however, no golden standard regarding screening for RIHD.

Radiotherapy with protons have emerged as a potential possibility to achieve local control and eventually reduce the risk for late toxicity and secondary tumors. From early on, thymic malignancies was recognized as a group who would eventually benefit from proton therapy (20-21). Treating thoracic malignancies with protons is cumbersome because of many reasons; tumor and organs at risk motion may result in interplay effects which compromise dose distribution being one of them. Movement of mediastinal structures occurs but seems to

be minor compared to the movement in the lung parenchyma and patients with Hodgkins' disease has been successfully treated with protons. TETs are generally located in close proximity to the mediastinum. Recent years more and more data have been published showing superior dose distribution and feasibility regarding toxicity while treating thymomas with protons (22-24). The majority of previous thoracic proton therapies have been given with passively-scattered technique. At the Skandion Clinic all patients will be treated with pencil beam scanning (PBS) with proton energies ranging from 60 to 230 MeV. This technique may further optimize dose distribution although planning, quality assurance and motion management is even more crucial (25-26).

## **4.0 Rationale and Objective of the study**

### **4.1 Objective**

To explore whether proton radiotherapy is feasible and results in an acceptable local control

#### **4.1.1 Primary Objective**

Toxicity (eg cardiac and pulmonary toxicity).

Local control at 5 years. Local control is defined as freedom of locally progressive disease; ie CR (complete remission) or SD (stable disease) based on CT or PET/CT evaluation

#### **4.1.2 Secondary Objective**

Overall survival, progression-free survival, relapse pattern, quality of life measured with QLQ 30 + LC 14.

## **5.0 Study Design**

### **5.1 Description**

This is an open, non-randomized multicentre, phase II trial, to investigate the efficacy and toxicity in PBS proton therapy of thymic malignancies

### **5.2 Time Schedule**

The trial is expected to start after Ethics Committee has approved the protocol.

Target recruitment period is estimated to be 60 months.

End date is estimated to be five years from last treatment.

### **5.3 Treatment Schedule**

The study population will consist of three patient categories;

**A** patients who have undergone radical surgery

**B** patients who have undergone non-radical surgery

**C** patients who are considered inoperable.

Radiotherapy doses will differ between the groups. We have assumed that RBE for protons is 1.1 and the prescribed dose is the corresponding dose for photons (Gy(RBE)). Within brackets is the physical dose.

Patients who have undergone radical surgery but has an unfavorable histology (B2, B3, C) and/or Masaoka stage III or IVa (selected stage II-patients can be considered according to local practice) will receive 2 Gy(RBE) once daily, five days a week to a total dose of 50 Gy(RBE) (1.82 Gy OD, total dose 45.5 Gy)

Patients who have undergone non radical surgery (R1), regardless of stage and histology, will receive 2.3 Gy(RBE) once daily, five days a week, to a total dose of 57.5 Gy(RBE) (2.09 Gy OD, total dose 52.25 Gy)

Patients who are considered medically inoperable, or refuses surgery, regardless of stage and histology, and patients who have undergone R2 non-radical resection will receive 2.5 Gy(RBE) once daily, five days a week, to a total dose of 62.5 Gy(RBE) (2.27 Gy OD, total dose 56.75 Gy)

Patients not willing to participate in study, but willing to be included in follow-up according to study protocol will receive photon therapy according to local practice. The total dose must be  $\geq 45$  Gy.

Up to three cycles of chemotherapy may be administered prior to start of radiation according to local practice. Radiation therapy shall then start within 4-6 weeks after completion of the third cycle. Use of concomitant chemotherapy is not allowed.

If surgery has been performed, radiation therapy shall start 4-8 weeks thereafter

## **5.4 Treatment duration**

The radiotherapy overall treatment time in all of the patient categories should preferably be five weeks. In case of interruptions for either technical or administrative reasons the treatment time should not exceed six weeks. If protons cannot be delivered in stipulated six weeks, photon backup plan shall be used instead.

## **5.5 Reason for discontinuation of treatment**

- Progressive disease under any time of treatment is reason for stopping the treatment
- Adverse reaction that is severe or life threatening that precludes further treatment.
- Major protocol violations such as unjustified substantial modifications of the radiotherapy treatment.
- Missing essential data as for safety and/or efficacy assessment that cannot be recovered are missing
- Patient refusal, or withdrawal of informed consent.

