	
On treatment evaluation:
 
 
• Recording of toxicity, performance status, ECG, NT-ProBNP, TNT, CRP at week 3 and end of treatment.
 
• Weight weekly. If weight change >5%, a new CT-scan and replanning should be considered.
 
• QLQ30 + LC14 at end of treatment
 
• At end of treatment visit patient shall be referred to TTE/UCG which shall preferably be performed one week after completion of therapy, but at least within two weeks
 
 
Follow up assessment:
 
First follow-up 4 weeks after completion of therapy and three months thereafter. Then every three months during the first two years. Thereafter every six months until end of study
 
 
• Recording of persistent or new toxicity
 
• Performance status
 
• Weight
 
• Tumour response evaluation with CT scan at 4, 7, 13 months and every 6 months thereafter or if clinically indicated.
 
• Spirometry including CO diffusion capacity at 6 months
 
• ECG at each visit the first year. Thereafter annually or if clinically indicated
 
• Cardiac markers: NT-ProBNP, TNT
 
• Quality of life according to QLQ30+LC14 at baseline, week 3 during treatment, 1, 3, 6 and 12 months after completed radiotherapy. Thereafter at 2, 3 and 5 years after treatment.
 

Statistical methods:	We will perform a Kaplan-Meier analysis with the aim to compare our data with published historic data from the ITMIG international database and other datasets. Toxicity data will be analysed descriptively and there will be a comparison between the proton patients and photon control group. 40 patients will be included in the study

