### **5.13 Ethics**

The study will start after approval from authority and Ethical committee and it is the responsibility of the Investigator-Sponsor to supply the co-investigators with a copy of the final assessment. This study will be conducted in compliance with the protocol and in accordance with the ethical principles put forward in the Declaration of Helsinki and in accordance with GCP rules.

The rights, safety and well-being of the trial subjects are the most important considerations and should prevail over interests of science and society.

Study personnel involved in conducting this trial will be qualified by education, training and experience to perform their respective tasks.

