## **7.2 On Treatment evaluation**

- Recording of toxicity and performance status, at week 1, 3 and 5 during treatment
- Weight every week
- Registration of volumes for GTV, PTV, constraints doses to normal tissues: Lung:  $V_5$ ,  $V_{20}$ ,  $V_{40}$ , MLD. Esophagus:  $D_{2\%}$ , mean dose. Heart: mean dose,  $V_{40}$ . LADCA:  $D_{2\%}$ , mean dose Spinal cord:  $D_{2\%}$

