## 8.0 Radiotherapy

All patients included in the study must be able to receive prescribed dose to the target volume without exceeding absorbed doses to the organs at risk. Dose planning shall be performed with a CT-based system. A 4DCT for the planning is mandatory and has to be repeated before start of treatment. If tumour motion exceeds 0.5 cm proton therapy will not be given. All patients needs to have a photon backup plan, preferably with IMRT/VMAT technique although 3DCRT is allowed. Treatment planning can be performed on either average CT from the 4D-CT or a regular CT. Slice thickness is to be maximally 3 mm. If the photon plan is superior to the proton plan, the photon plan is to be used and the patient will be excluded from the study and followed up according to the photon cohort protocol.

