## **8.7 Interruption of radiotherapy**

After radiotherapy starts, efforts should be made to avoid interruptions in the planned schedule. If an interruption must be made due to technical or administrative reasons the following policy will be applied. At least four fractions a week must be given. If this is not possible with protons the photon backup plan must be used. Try to maintain the total treatment time as close to 5 weeks as possible.

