## **9 Adverse events**

### **9.1 Definition**

#### **Adverse events (or adverse experience) (AE):**

An AE is any untoward medical occurrence in a subject or clinical investigation subject treated within a study protocol and which does not necessarily have a causal relationship with this treatment.

An AE can therefore be any unfavorable and unintended sign (including an abnormal laboratory finding, for example), symptom, or disease temporally associated with the radiation treatment, whether or not considered related to the radiotherapy

Due to regulatory requirements, events occurring during pre- and post-treatment periods should also be designated as AEs. Therefore, safety surveillance - reporting of (S)AEs - commences at the time when the subject is enrolled into the study (date of signature of the informed consent) until the End of Study Visit has been performed.

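### Section 5.5 makes unrecoverable missing data a reason to stop radiotherapy; this is most likely a misplaced evaluability criterion and should come out of the list

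*Protocol*

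**What the plan says.** Protocol section 5.5 is headed as a list of reasons for discontinuing treatment. Four of its five items are progression during treatment, a severe or life-threatening adverse reaction, a major protocol violation, and patient refusal or withdrawal of consent. The remaining item, fourth in the list, reads: "Missing essential data as for safety and/or efficacy assessment that cannot be recovered are missing". The protocol does not say which data are essential, and no other section limits the item.

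Section 5.7 (Stopping Rules) uses the same list a second time. It describes patients who leave under 5.5 as dropouts, and too many of them is a ground for stopping the trial. Section 5.8 defines completion by 40 evaluable patients who were treated according to the protocol and followed for 60 months.

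Two other sections bear on the item. Section 5.13 (Ethics) says: "The rights, safety and well-being of the trial subjects are the most important considerations and should prevail over interests of science and society". Section 8.7 says that efforts should be made to avoid interruptions once radiotherapy has started.

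**The concern.** A gap in the research record gives no clinical reason to stop a postoperative or definitive course of radiotherapy. Yet the item stands, without qualification, beside progression and life-threatening reactions in a list that sites consult when deciding whether to stop. A site that applied the list literally could end a patient's course for a reason that has nothing to do with that patient's interest.

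There is also a smaller problem. One list does two jobs: it governs the end of treatment and, through 5.7, it defines dropouts. Stopping radiotherapy and leaving the study are different events. The protocol should not leave sites to guess whether a patient who has the first is also meant to have the second.

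**Working it through.** No figure in the protocol rests on this item, so there is nothing to recompute. The check sets the relevant sections side by side.

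1. **Is the list about stopping treatment?** Yes. The heading of 5.5 says so, and its first item speaks of stopping the treatment.

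2. **Does any section narrow the missing-data item?** No. Nothing confines it to evaluability, and nothing says that radiotherapy continues when data are missing. Section 5.7 shows a second use of the list but does not withdraw the first.

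3. **What was probably meant?** Local control is judged on CT or PET/CT (4.1.1). Tumour assessment by CT is scheduled before inclusion and next at 4 months after therapy (5.6, 7.3 and Table 1). The control CTs during treatment in 8.6 serve dose checking and re-planning. So no scheduled efficacy scan falls within the five-week course, and the efficacy half of the item can hardly work as a mid-course stop. With the dropout wording in 5.7, this points to a misplaced evaluability criterion.

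4. **Could the safety half operate during treatment?** In principle yes, because safety data are collected then, but clear examples are hard to find.
   - The synopsis has "Recording of toxicity, performance status, ECG, NT-ProBNP, TNT, CRP at week 3 and end of treatment", which fixes week 3 for ECG and cardiac markers. Section 7.2 lists neither, and Table 1 asks for them during radiotherapy without naming a week. A missed week-3 sample is therefore not clearly unrecoverable.
   - For toxicity, section 7.2 has "Recording of toxicity and performance status, at week 1, 3 and 5 during treatment", and 9.2 requires start and stop dates for each event. One missed toxicity record can largely be reconstructed.

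5. **Does the photon backup plan cover the case?** Section 8.0 says "All patients needs to have a photon backup plan". Its stated uses are treatment that cannot be delivered within six weeks (5.4), tumour motion above 0.5 cm (8.0 and 8.6), and fewer than four fractions a week, where 8.7 says "If this is not possible with protons the photon backup plan must be used". Section 8.0 also has the photon plan used when it is superior to the proton plan. None of these is missing data.

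6. **Does follow-up continue after a stop under 5.5?** Largely, as far as the text goes. Adverse-event reporting runs "until the End of Study Visit has been performed" (9.1), and 9.4 repeats the duty to follow up. Footnote 1 of Table 1 continues CT during follow-up or until progression, so progression is its only stated early end. No section says expressly that patients who stop under 5.5 keep to this schedule, and 5.7 calls them dropouts.

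**The case against.** The strongest reply is that this is a garbled, misplaced line that no investigator would use to halt radiotherapy. Section 5.13 says which consideration wins when patient and research interests collide, 5.5 lists a reason without ordering a stop, and the schedule of scans shows that the item makes sense only as an evaluability criterion. Much of this stands. The intent is probably as described, the conflict with 5.13 is inferred from a general principle, and the practical risk is small. But a general principle does not remove an item from a list that sites are told to use.

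Two stronger readings are tempting, and the documents support neither.

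- A reader might infer a specific under-dosing risk by counting the fractions undelivered after a mid-course stop, or by comparing the delivered dose with the minimum total dose set in 5.3 for the photon cohort. Such a count would describe any mid-course stop, whatever its cause, and would assume that no further radiotherapy is given. Nothing bars completing the course outside the protocol. The photon-cohort minimum is a condition for that cohort, not a standard of adequacy for an interrupted proton course.
- A reader might infer that these patients are lost from the local-control evaluation. Sections 5.7 and 5.8 are rules for stopping and completing the trial and define no analysis set. How discontinued patients are analysed is commonly left to the statistical analysis plan, and CT and adverse-event follow-up have no stated end at treatment discontinuation.

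**Conclusion.** The point holds as a minor drafting defect that touches patient care. As written, unrecoverable missing data are a reason to discontinue radiotherapy. That is not a clinical reason, and it runs against 5.13 and 8.7. The likely explanation is a misplaced evaluability criterion.

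The frequency cannot be derived, because the protocol gives no rate of missing data; it is probably low. No stated sample size, endpoint or analysis changes. The conclusion rests on reading 5.5 according to its heading and first item, and on finding no section that limits the missing-data item. On follow-up, the defect is only that the protocol does not expressly separate stopping treatment from leaving the study.

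**What to change.** Make three changes in an amendment:

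- Delete the missing-data item from 5.5.
- State that such cases are recorded as protocol deviations and that radiotherapy continues unless there is a clinical reason to stop or the patient refuses.
- State that patients who stop treatment under 5.5 remain in scheduled follow-up, including CT, unless they withdraw consent to follow-up.

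The cost is one deleted line and one or two added sentences, with no change to the design. The small downside is that some patients with incomplete data stay in the analysis. Because 5.7 counts dropouts by reference to 5.5, the deletion also takes missing-data cases out of that stopping rule. If the sponsor wants data loss to count there, 5.7 should name it directly.

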## **5.6 Follow-up**

First follow-up 4 weeks after completion of therapy, then at four months and every three months thereafter for the first year, then every six months for a maximal five years in total.

Recording of persistent or new toxicity, performance status and weight will be done at all visits.

Tumour response evaluation with CT scan will be done at 4, 7, 10 and 13 months after therapy and every 6 months thereafter or if clinically indicated.

Quality of life according to QLQ30 + LC 14 will be measured at baseline, week 3 during treatment, and of treatment, 1, 3, 6 and 12 months after completion of radiotherapy. Thereafter at 2, 3 and 5 years after treatment. The administration of the questionnaires will be handled centrally by the Clinical Trial Unit at the Oncology Department, Sahlgrenska University Hospital.

Spirometry including CO diffusion capacity will be repeated at 6 months after therapy and at end of study

UCG will be performed within two weeks after completion of therapy and at end of study, i e 5 years after treatment

ECG will be recorded at each visit

## **5.7 Stopping Rules**

The trial will stop prematurely for the following considerations:

- If emerging toxicities are of such a serious nature that continuation of the trial becomes unacceptable.
- If the recruitment is too low to expect completion of the study in its present form within an acceptable period of time (inclusion estimated to be 60 months)
- If the number of dropouts as described above (5.5) is too high and this situation cannot be acceptable for a period of time.

## **5.8 Ending and completion of the study**

The study is finished when an estimated number of 40 evaluable patients have completed the treatment according to the protocol and are followed for 60 months.

## **5.9 Patient registration**

Before patients agree to participate in this trial all patients will be given oral and written information. A "Patient information sheet" and a consent form, prepared in the local language will be handed out to the patients. The formal consent form must be signed and dated by the patients and investigator before they are submitted to any study-specific procedure.

Patients that fulfil the eligibility criteria and have signed and dated the formal consent will be registered by phone to the Clinical Trial Unit, Sahlgrenska University Hospital, Göteborg at [contact]. Treatment should start within four weeks from registration.

